7. STUDY POPULATION

7.1. Patient Disposition

Patient disposition will be summarized for the Enrolled Analysis Set by treatment group and overall total. The summary will include:

- Number of patients screened.
- Number of screen failures, i.e., screened but not randomized, with reasons for screen failure. The denominator for percentage of screen failures will be the number of patients screened. The denominator for percentages for reasons for screen failures will be the number of screen failures.
- Number randomized. The denominator for percentage of randomized patients will be the number of patients screened.
- Number randomized and not treated. The denominator for percentage of randomized and not treated patients will be the number of patients randomized.

- Number in each analysis set. The denominator for percentage in each analysis set will be the number of randomized patients. In addition, the number of patients randomized to the PK/PD substudy will be presented.
- Number who discontinued treatment early and reason(s) for discontinuation of treatment. The denominator for percentages will be the number of randomized and treated patients (Efficacy Analysis Set).
- Number who discontinued from study prior to completing the study and reason(s) for discontinuation. The denominator for percentages will be the number of randomized and treated patients (Efficacy Analysis Set).

A by-patient data listing of study disposition information including the reasons for treatment and/or study termination will be presented. Withdrawal of consent details will also be included, if applicable.

A by-patient data listing including the reasons for exclusion from each analysis set will be presented.

7.2. Demographics and Baseline Characteristics

Demographic variables will include the following:

- Age at informed consent including the subgroup of <65 years vs ≥ 65 years
- Sex
- Race
- Ethnicity

Other baseline characteristics will include the following:

- Weight (kg)
- Height (cm)
- BMI (kg/m^2) including the following subgroup: <30, ≥ 30 - <35, ≥ 35 - <40, ≥ 40 kg/m^2
- Waist circumference (cm)
- Baseline liver stiffness by transient elastography (kPa)
- Baseline Controlled Attenuation Parameter (CAP; dB/m)
- Baseline LFC (%) by MRI-PDFF
- Baseline cTI (msec) by MRI including the following subgroup: Low (<800 msec), Elevated (800 – 875 msec), and High (>875 msec).
- Liver Biopsy within 2 years of randomization
 - Baseline fibrosis stage (F1, F2, F3)
 - Baseline NAFLD Activity Score (NAS)

- Baseline Comorbidities will be based on Medical History case report form, Medical Dictionary of Regulatory Activities (MedDRA) preferred term (PT)
 - Diabetes status (yes, no) will be defined as PT preferred term (PT) includes “diabetes mellitus” or “Diabetic neuropathy” will be assigned yes, otherwise no.
 - Hypertension (yes, no) will be defined as PT of “Hypertension” will be assigned yes, otherwise no.
 - Dyslipidemia (yes, no) will be defined as Standardized MedDRA query (SMQ) of “Dyslipidemia (SMQ)” will be assigned yes, otherwise no.
- Baseline medication use, defined as starting prior to first administration of study drug, regardless of end date:
 - Statins defined by the WHODD Standardized Drug Grouping (SDG) of “Statins”
 - Antihypertension medications defined by the WHODD SDG of “Antihypertensives”
 - Antithrombotic medications defined by WHODD SDG of “Antithrombotic drugs”
 - Antidiabetic medications defined by the WHODD SDG of “Drugs used in diabetes”
 - NASH Medications, defined as the following medications with potential beneficial effect on NASH:
 - Vitamin E defined by the WHODD drug codes beginning in “001105” or if “VITAMIN E” is found in the preferred drug name
 - Obeticholic acid defined by WHODD drug codes of 064968 01 001 through 064968 01 003
 - Pioglitazone or other PPAR γ agonists defined by WHODD ATC level 4 A10BD and A10BG
 - GLP-1 analogues defined by WHODD ATC level 4 code (term) A10BJ (Glucagon-like peptide-1 [GLP-1] analogues)
 - DPP-4 inhibitors defined by WHODD ATC level 4 code (term) A10BH (Dipeptidyl peptidase 4 [DPP-4] inhibitors)
 - SGLT2 inhibitors defined by WHODD ATC level 4 code (term) A10BK (Sodium-glucose co-transporter 2 [SGLT2] inhibitors)
 - Steatohepatitis Medications, defined as the following medications that may potentially worsen steatohepatitis:
 - Corticosteroids (of > 10 mg/day for > 2 weeks [prednisone or prednisone equivalent dose ([Appendix 1](#))]) defined by WHODD ATC level 2 code (term) H02 (Corticosteroids for Systemic Use)
 - Amiodarone defined by WHODD drug codes 001331 01 001 through 001331 01 029 and 001331 02 001 through 001331 02 250
 - Tamoxifen defined by WHODD drug codes of 003887 01 001 through 003887 01 020 and 003887 02 001 through 003887 02 273

- Methotrexate defined by WHODD drug codes of 001138 01 001 through 001138 01 172 and 001138 02 001 through 001138 02 189

The following baseline laboratory tests will be summarized as continuous variables and as frequencies for categorizations described:

[figure not shown]
- Baseline ALT level (IU/L):
 - \leq 60 U/L versus $>$ 60 U/L (overall and by sex)
 - $<$ 2x ULN versus \geq 2x ULN to $<$ 5x ULN
- Baseline AST level (IU/L): The same subgroups as specified for ALT above will be used.
- Baseline GGT level (IU/L): \leq ULN, $>$ ULN
- Baseline ALP level (IU/L): \leq ULN, $>$ ULN
- Baseline total bilirubin level (mg/dL): \leq ULN, $>$ ULN
- Baseline fasting HDL cholesterol (mg/dL)
- Baseline fasting LDL cholesterol (mg/dL)
- Baseline fasting total cholesterol (mg/dL)
- Baseline fasting triglycerides (mg/dL)
- Baseline fasting glucose level (mg/dL)
- HbA1c (%): $<$ 6.5%, \geq 6.5%
- Baseline platelet count (10^9 /L):
 - $<$ 75, \geq 75 \times 10^9 /L
 - $<$ LLN, \geq LLN to \leq ULN, $>$ ULN

Demographics and baseline characteristics will be summarized by treatment group and overall, for Efficacy, Safety, PP, and Treatment Completer Analysis Sets. The PP and Treatment Completer Analysis Sets will only be presented if the analysis set differs from the Efficacy Analysis Set by more than 10 patients total.

All demographic and baseline characteristics data will be presented in by-patient data listings.

No inferential statistical comparisons will be performed.

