9. ALP > 156 IU/L

10. Platelet count < 150,000 /mm³

11. eGFR < 60 mL/min/1.73m²

12. Weight loss of > 5% total body weight within 3 months prior to Screening

13. History of a malignancy within 2 years of screening, with the following exceptions:

- a) Adequately treated carcinoma in situ of the cervix
- b) Adequately treated basal or squamous cell cancer or other localized non-melanoma skin cancer

[figure not shown]
14. Uncontrolled diabetes with HbA1c > 9.5%. [REDACTED]

15. Unstable cardiovascular (CV) disease defined as myocardial infarction, unstable angina, percutaneous intervention, coronary artery bypass graft, or stroke within 6 months prior to randomization

16. Uncontrolled hyperlipidemia defined as fasting LDL \geq 150 mg/dL despite treatment or total triglycerides > 300 mg/dL

17. QTc > 450 ms for males, > 470 ms for females

18. Known allergy to study drug

- 
20. Average weekly alcohol consumption of > 21 standard drinks for males and > 14 standard drinks for females over a period of more than 3 consecutive months in the year prior to Screening. Remote history of alcoholism with abstinence > 12 months prior to Screening and no history of alcoholic liver disease is permissible.

Note: A standard drink is defined as 12 oz (360 ml) beer, 1.5 oz (45 ml) liquor, or 5 oz (150 ml) wine.

21. Illicit substance/chemical abuse in the 12 months prior to Screening
22. Cannabis use (tetrahydrocannabinol [THC] and cannabidiol [CBD]) within 14 days of randomization
23. Unwilling to abstain from excessive alcohol use (defined in #20 above), cannabis use, and illicit substance use during study participation
24. Contraindications or inability to complete MRI scanning (ie, weight restrictions, presence of permanent pacemaker, implanted cardiac devices, etc.)
25. Positive for human immunodeficiency virus (HIV) infection
26. Laboratory or clinical evidence of current infection with Severe Acute Respiratory Syndrome Coronavirus 2 (SARS-CoV-2), i.e. COVID-19
27. Presence of any condition that could, in the opinion of the investigator, compromise the patient's ability to participate in the study

Prior or Anticipated Therapy

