8.8.3.3. Nonalcoholic Fatty Liver Disease (NAFLD) Fibrosis Score

The Nonalcoholic Fatty Liver Disease (NAFLD) fibrosis score will be calculated as: $-1.675 + 0.037 \times \text{Age (years)} + 0.094 \times \text{BMI (kg/m}^2\text{)} + 1.13 \times \text{baseline diabetes status (yes = 1, no = 0)} + 0.99 \times \text{AST/ALT ratio} - 0.013 \times \text{Platelet Count (10}^9\text{/L)} - 0.66 \times \text{Albumin (g/dL)}$. Age at informed consent and baseline diabetes status will be used. BMI at each visit will be calculated using the weight from that visit and height from screening. The baseline weight will be used for Week 2 since weight is not collected at Week 2. Lab values at each visit, from the same visit, will be used. Programming will calculate the score at each to be used in analyses. The NAFLD fibrosis score will be calculated at baseline and at Week 6, Week 12, and Week 16.

The NAFLD fibrosis score will be analyzed in the same manner as specified in [Section 8.8.3](#).

| | |
|------------|------------|
| [REDACTED] | [REDACTED] |

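### The baseline diabetes flag recognises only two pieces of medical-history term text, so a diabetic recorded another way could be labelled non-diabetic and score 1.13 too low on the NAFLD fibrosis score at every visit

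*SAP*

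**What the plan says.** SAP 7.2 takes the baseline comorbidities from the Medical History form, using MedDRA preferred terms. For diabetes it states "Diabetes status (yes, no) will be defined as PT preferred term (PT) includes" *diabetes mellitus* or *Diabetic neuropathy*, and such a patient "will be assigned yes, otherwise no". Hypertension is handled more narrowly: "Hypertension (yes, no) will be defined as PT of" the single term *Hypertension*, again with no as the default. The third comorbidity uses a broader method: "Dyslipidemia (yes, no) will be defined as Standardized MedDRA query (SMQ) of" *Dyslipidemia*.

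The same section reports HbA1c in two categories (below 6.5%, and 6.5% or more) and baseline drug classes, including "Antidiabetic medications defined by the WHODD SDG of" *Drugs used in diabetes*. Neither enters the diabetes flag.

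SAP 8.8.3.3 then uses the flag in the NAFLD fibrosis score, coded 1 or 0 and multiplied by 1.13: "Age at informed consent and baseline diabetes status will be used". The score is computed at baseline and Weeks 6, 12 and 16. It is analysed as in SAP 8.8.3, that is, by ANCOVA on change and separately on percent change, with baseline as covariate.

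**The concern.** A closed rule with a default of no is only as good as its list of terms. This list names one diabetic complication (neuropathy) and sends every other diabetic term lacking the words *diabetes mellitus* to no. It also leaves out a drug taken for diabetes, although protocol 6.6 records each medication's reason for use.

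Diabetes is expected in this population. Protocol 5.2 permits stable metformin and other antidiabetic drugs, and exclusion 14 is directed at poor control ("Uncontrolled diabetes with HbA1c > 9.5" per cent) rather than at diabetes as such. At stake are the diabetes row of the baseline table and, through the weight of 1.13, the value of one exploratory fibrosis score for any patient missed.

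**Working it through.** **Inputs.** The score formula and its coefficients are in SAP 8.8.3.3; the arm size of 24 is in SAP 2.2.4; the analysis of change and percent change is in SAP 8.8.3. The number of missed diabetics, *m*, is in neither document and is treated as an assumption.

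**1. What the rule returns.**
- A history term of *Type 2 diabetes mellitus* gives yes.
- No matching term gives no, whatever the HbA1c or drug record shows.
- A diabetic complication term other than neuropathy, without the words *diabetes mellitus*, gives no.

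**2. Effect on one patient's score.** The formula is

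−1.675 + 0.037 × age + 0.094 × BMI + 1.13 × diabetes + 0.99 × AST/ALT − 0.013 × platelets − 0.66 × albumin.

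Holding all else fixed, changing the flag from 1 to 0 lowers the score by exactly 1.13. Baseline status is used throughout, so the shortfall is the same at all four scored times. On the formula's own scale, 1.13 is worth 1.13/0.037 = 30.5 years of age, 1.13/0.094 = 12.0 kg/m² of BMI, or 1.13/0.013 = 86.9 × 10⁹/L of platelets. These figures only rescale the coefficient and say nothing about how many patients are affected.

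**3. Change and percent change.** Take an illustrative diabetic patient with assumed values: age 55; at baseline BMI 35, AST 45, ALT 60, platelets 230, albumin 4.3; later BMI 34.5, AST 38, ALT 45, platelets 225, albumin 4.3.

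| Flag | Baseline | Later | Change | Percent change |
|---|---|---|---|---|
| 1 (correct) | −0.306 | −0.194 | 0.112 | −36.5% |
| 0 (missed) | −1.436 | −1.324 | 0.112 | −7.8% |

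The constant cancels in the change. It does not cancel in the percent change, because it sits in the denominator. The percentages are negative although the score rose, because the baseline score is negative. Percent change in this score is therefore awkward to read whichever flag is used.

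**4. Effect on an arm mean.** The shortfall is 1.13 × *m*/24.

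| *m* missed in the arm | Arm mean too low by |
|---|---|
| 0 | 0 |
| 1 | 0.047 |
| 2 | 0.094 |
| 3 | 0.141 |
| 5 | 0.235 |

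**5. Effect on the ANCOVA of absolute change.** The outcome is untouched, but the baseline covariate is wrong for missed patients. To first order, one missed patient in one arm moves the adjusted difference by 0.047 times the baseline slope. The documents give no value for that slope.

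**The case against.** The strongest reply is that the documents do not show that anyone would be missed. Medical history collects illnesses and medication history (protocol 8.1.3), and most diabetics may well have a term containing *diabetes mellitus*. The SAP is dated 19 May 2021, a year after protocol Amendment 1, and its COVID-19 section describes study events in the past tense. A single named complication would fit a list built from terms already coded in this trial, in which case the list could be complete. The documents do not settle this, so the number missed may be zero.

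Much would also be visible elsewhere. All medical history is tabulated by preferred term, and HbA1c and drug classes have their own rows. A recorded diagnosis, a laboratory value and a prescription measure different things, so disagreement among them is not in itself a contradiction. The documents use HbA1c of 6.5% or more as a summary category and do not say that it defines diabetes. Protocol Appendix 1 has HbA1c collected only at Screening. An antidiabetic drug may have another indication.

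These replies limit the size of the problem. They do not remove it: as written, the rule gives a wrong score for any diabetic recorded only under another term, and the text does not say that the list was checked for completeness.

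Two stronger readings should be resisted. A reader might infer that patients with HbA1c of 6.5% or more, or on treatment for diabetes, are generally labelled non-diabetic; in fact only those with no matching history term are. A reader might also infer that exclusion 14 admits anyone with HbA1c up to 9.5% regardless of recorded history; text after that criterion is redacted, so this cannot be concluded.

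**Conclusion.** The point holds as a minor weakness in a stated derivation. A diabetic patient with no matching preferred term would be labelled non-diabetic, and that patient's NAFLD fibrosis score would be 1.13 too low at baseline and Weeks 6, 12 and 16. The arm mean falls by 0.047 for each such patient in an arm of 24. Score levels, the baseline covariate and the percent-change ANCOVA are affected; absolute change itself is not.

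The size in this trial rests entirely on the unknown number missed. It cannot be said that the baseline table does understate diabetes, only that it could. Nor do the documents support a claim that a main treatment comparison is compromised: the score is exploratory, testing is nominal under SAP 8.6, and no primary or secondary endpoint uses the flag. The visible SAP sets no cut-off on this score, so a shifted level reclassifies nobody. The hypertension flag has the same narrow form, but in the visible text it feeds only a descriptive table.

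**What to change.** Before unblinding, revise the diabetes definition in SAP 7.2 so that a patient is counted as diabetic if either of these holds:

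- any Medical History preferred term is on a reviewed list of diabetes and diabetic-complication terms (or falls in a standardized query, as is done for dyslipidemia);
- a baseline antidiabetic drug has diabetes as its recorded reason for use.

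Cross-check the result against screening HbA1c of 6.5% or more and footnote any discordant patients. HbA1c serves here as a check; making one value part of the definition would be a matter of preference. Use the revised flag in SAP 8.8.3.3. The hypertension flag can be broadened the same way if wanted.

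The cost is a change of SAP wording, one review of coded terms and a small derivation from data already collected. The downside is a possible few false positives.

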7.3. Protocol Deviations

7.4. General Medical History

All medical history conditions will be coded using the Medical Dictionary of Regulatory Activities (MedDRA). Medical history will be summarized by treatment group and overall total by system organ class and preferred term, using the Safety Analysis Set. Summaries will be ordered by descending order of the overall incidence of system organ class and preferred term within each system organ class.

7.5. Prior and Concomitant Medications

Prior medications are defined as medications that started before first study drug administration and either stopped before or continued after first study drug administration. Concomitant medications are defined as medications that are being taken while on study drug through 30 days after last dose or through the Follow-Up Period (Week 16). Medications that are ongoing on the date of the first administration of study drug will be classified as both prior and concomitant. Any medication that cannot be confirmed as stopping before the start of study drug will be classified as both a prior and a concomitant medication. Imputation of partial dates is defined in [Appendix 2](#).

Prior and concomitant medications will be summarized separately and the number and percentage of patients in each treatment group who took at least one prior (concomitant) medication as well as the number and percentage of patients who took each type of medication will be summarized by Anatomic Therapeutic Class (ATC) Level 2, ATC Level 4, and preferred name for the Safety Analysis Set. If a patient has more than one occurrence of the same preferred name, then the preferred name will be counted only once for that patient. Similarly, if a patient has more than one preferred name within ATC Level 4 or ATC Level 4 within ATC Level 2, then the patient will be counted only once in that ATC Level 4 or ATC Level 2.

Any medications with potential impact on NASH outcome and steatohepatitis will be presented in a separate by-patient listings.

8. EFFICACY ANALYSES

8.1. Adjustments for Covariates

For comparison of treatment groups with respect to change and percent change from baseline, analysis of covariance (ANCOVA)

will be used. The corresponding baseline value will be used as a covariate in the model.

8.2. Handling of Dropouts or Missing Data

Primary analyses will be based on observed data.

8.3. Interim Analyses and Data Monitoring

8.4. Multicenter Studies

The randomization is not stratified by site. Likewise, analyses of data will not be stratified by study site.

8.5. Use of an “Efficacy Subset” of Patients

Not Applicable.

8.6. Multiple Comparisons/Multiplicity

There will be no adjustment for multiplicity. Statistical testing will be considered nominal, descriptive, and exploratory.

8.7. Secondary Efficacy Analyses: Percent Change from Baseline in ALT Levels at Week 12

Descriptive statistics of ALT values, change from baseline, and percent change from baseline values will be presented by treatment group for each visit using the Efficacy Analysis Set. In addition, figures of mean (\pm SD) ALT values, change from baseline, and percent change from baseline will be presented over time by treatment group.

Analyses of percent change (and separately change) from baseline will be carried out using an ANCOVA model at Week 12 with percent change (and separately change) from baseline as the dependent variable including treatment group as a fixed effect and baseline as a covariate. The primary analysis of percent change (and separately change) in ALT at Week 12 will be carried out using available observed data only, without imputation for missing data.

The estimates of least-square (LS) means, standard errors (SE), and 90% and 95% CIs will be presented by treatment group. Estimates of the LS mean difference between pooled TERN-101 (All TERN-101) and placebo, and each pairwise comparison between placebo and each active dose of TERN-101, will be presented with the associated standard error of the difference, and 90% and 95% CIs of the difference.

The same ANCOVA model will be used to analyze the last on-treatment value for Week 12, to be labelled as “End of Treatment”. For patients who complete Week 12, the Week 12 value will be used. For patients who do not complete treatment, the last value on treatment will be used.

The same ANCOVA model will be presented for each post-baseline visit using observed data only.

The distribution of percent change values will be evaluated visually for normality assumptions. If normality assumptions are violated, i.e. data are not normally distributed, a Wilcoxon Rank Sum Test will be used to compare each TERN-101 dose to placebo, and pooled TERN-101 (All TERN-101) to placebo. The median differences and 90% and 95% CIs of the median differences between treatment groups will be constructed using Hodges-Lehmann estimate.

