1.3. Schedule of Activities (SoA)

Visit	Screening	Treatment Period ^d							Follow-Up ^b	ET ^a	Notes
		Week 0	Week 2	Week 4	Week 6	Week 8	Week 12	Week 16			
Study Day	-56 to Day -1	Day 1	15	29	43	57	85	113		Visit windows post randomization through Week 12: ± 3 days from the specified study day. Visit window Week 16: -1 week /+2 days from the specified study day.	
Procedures											
Written Informed Consent	X									Written informed consent may be obtained via telephone in accordance with Section 10.1.2. Screening may be initiated via telephone to avoid a visit to the site, if the patient is disqualified based on medical history.	
Patient Fasting	X	X	X	X	X	X	X	X	X	Patients must be in fasted state for at least 8 hours prior to blood collection and treatment administration where applicable.	
Randomization		X									
Review Inclusion and Exclusion Criteria	X	X								Recheck clinical status before randomization and first dose of study drug.	
Demographics	X									Includes age, sex, and race/ethnicity.	
Height and Weight	X	X	X	X	X	X	X	X	X	Height and weight are collected at Screening and will be used to calculate BMI for eligibility. Waist circumference is also measured at Screening. Only weight is collected Week 0, 4, 6, 8, 12, 16, and ET.	
Medical history	X									Includes details of illnesses and allergies, date(s) of onset, whether condition(s) is currently ongoing, and medication history, including alcohol use.	
Physical Examination	X	X	X	X	X	X	X	X	X	A complete physical examination will be performed at Screening and Week 16. A targeted physical examination will be performed at all other visits.	

	Screening	Treatment Period ^e							Follow-Up ^b	ET ^a	Notes
		Week 0	Week 2	Week 4	Week 6	Week 8	Week 12	Week 16			
Visit	Screening										
Study Day	-56 to Day -1	Day 1	15	29	43	57	85	113			Visit windows post randomization through Week 12: ± 3 days from the specified study day. Visit window Week 16: -1 week /+2 days from the specified study day.
Vital Signs	X	X	X	X	X	X	X	X	X	X	Includes temperature, pulse rate, respiratory rate, and blood pressure.
Chemistry ^c	X	X	X	X	X	X	X	X	X	X	Specific analytes are listed in Appendix 1. ALT/AST stability may be evaluated prior to randomization per Section 5. Increased monitoring criteria for elevated ALT and/or AST above 2 × Baseline or above 5 × ULN for < 1 week is outlined in Appendix 3.
Hematology ^c	X	X	X	X	X	X	X	X	X	X	Refer to Appendix 5 for the eGFR formula, to be calculated by central lab.

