6. INR > 1.1
7. ALT or AST > 5 × ULN

8. Unstable elevated ALT or AST. Patients with ALT or AST > 60 IU/L must have evidence of a stable ALT/AST over at least a 2-week time period prior to randomization

[REDACTED]

[REDACTED]

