4.4. Data Conventions

The precision of original measurements will be maintained in summaries, when possible.

Quantitative safety laboratory tests containing less than (<) and greater than (>) symbols are test results that are below and above quantifiable limits, respectively. In order to retain these values for analysis purpose, the following will be imputed and stored within the analysis datasets:

- For values with <, the imputed value will be the numeric portion $\times 0.9$.
- For values with >, the imputed value will be the numeric portion $\times 1.1$.

PK and PD imputation of values below the limitation of quantitation (BLQ) are specified in [Section 8.9.1](#) and [Section 8.10.1](#), respectively.

Variables with a non-normal distribution that impacts the interpretation or validity of the planned analysis may have a data transformation applied (e.g., ln, \log_{10}).

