4.7.2. Definition of Baselines

The baseline value for statistical analyses of quantitative laboratory parameters is defined as the mean of all available evaluations, including any unscheduled or repeat assessments, prior to the first administration of study drug, unless otherwise specified. If there is only one evaluation prior to the first administration of study drug, then the available data from this evaluation will be used as the baseline value.

For glucose and lipid parameters, only assessments taken while fasting for 8 hours will be included in the baseline derivation.

The baseline value for analyses of qualitative parameters (e.g., normal/abnormal) is defined as the last evaluation prior to the first administration of study drug.

The baseline value for analyses of weight, body mass index (BMI), and electrocardiogram parameters is defined as the last evaluation prior to the first administration of study drug.

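### SAP 8.7: the non-normality fallback for Week 12 ALT is triggered by eye, drops the baseline covariate and has no stated standing against the ANCOVA; a baseline-adjusted rank test and a named lead analysis would be a cheap improvement

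*SAP*

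**What the plan says.** SAP 8.7 analyses percent change in ALT at Week 12 by ANCOVA "including treatment group as a fixed effect and baseline as a covariate", on observed data. SAP 8.1 likewise makes the corresponding baseline value a covariate when groups are compared on change or percent change.

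SAP 8.7 closes with a conditional rule: "The distribution of percent change values will be evaluated visually for normality assumptions". If the data are judged non-normal, "a Wilcoxon Rank Sum Test will be used to compare each TERN-101 dose to placebo", and also pooled TERN-101 to placebo, with Hodges-Lehmann median differences and 90% and 95% CIs. No baseline term appears in this fallback.

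SAP 4.4 offers a second remedy for the same problem: "Variables with a non-normal distribution that impacts the interpretation or validity of the planned analysis may have a data transformation applied".

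The 8.7 rule is reused by reference for liver fat (8.8.1.1), liver function tests (8.8.2) and NASH/fibrosis biomarkers (8.8.3), and is repeated for the PD markers in 8.10.3.

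Two passages bear on its weight. SAP 4.7.2 says the baseline for "quantitative laboratory parameters is defined as the mean of all available evaluations, including any unscheduled or repeat assessments" before first dose. SAP 8.6 says "Statistical testing will be considered nominal, descriptive, and exploratory".

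**The concern.** Three things are left open or lost.

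- **Trigger.** The readable text gives no criterion for failure, no assessor and no timing relative to unblinding.
- **Standing.** The text does not say whether the Wilcoxon result replaces the ANCOVA or stands beside it, nor which leads if they disagree.
- **Covariate.** Percent change already contains baseline, but it does not remove regression to the mean. Patients who start high tend to fall more. An arm that starts higher by chance therefore shows a larger fall with no drug effect. The ANCOVA corrects for this and the fallback does not.

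ALT is the only secondary efficacy endpoint, and PK is the other secondary endpoint. At stake are some precision, a chance shift in the reported effect, and freedom over which p-value to put forward.

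**Working it through.** The plan has no readable figure to reproduce. The power table is redacted, and Protocol 9.2 says the sample size was set without regard to power.

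**Inputs from the documents:** 24 per arm (Protocol 4.1); two-sided 0.05 (SAP 4.1); baseline as the mean of all pre-dose values (SAP 4.7.2); chemistry scheduled at Screening and Week 0 (Protocol 1.3), so normally two ALT values.

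**Assumed, not in the documents:** lognormal ALT with log-SD σ = 0.42; correlation ρ between single visits of 0.5, 0.7 or 0.85; true effect -20%, or ln(0.8) = -0.223.

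**Step 1. What the covariate removes.** On the log scale, ignoring truncation at the ALT entry limit, with a two-value baseline:

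- variance of baseline = σ²(1+ρ)/2
- slope of log ratio on baseline = 2ρ/(1+ρ) - 1
- residual variance with adjustment = σ²[1 - 2ρ²/(1+ρ)]
- variance without adjustment = residual variance + slope² × baseline variance

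| ρ | slope | adjusted (×σ²) | unadjusted (×σ²) | ratio | n per arm for Wilcoxon to match 24 adjusted |
|---|---|---|---|---|---|
| 0.5 | -0.333 | 0.667 | 0.750 | 1.125 | 27.0 |
| 0.7 | -0.176 | 0.424 | 0.450 | 1.063 | 25.5 |
| 0.85 | -0.081 | 0.219 | 0.225 | 1.028 | 24.7 |

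Simulation gives 24-28 per arm.

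**Step 2. Power gain over the unadjusted Wilcoxon.** Approximate power = Φ(0.223/SD × √12 × √(3/π) - 1.96), where SD is the square root of the variance in Step 1.

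- ρ = 0.5: 59.6% adjusted against 54.6%, a gain of 4.9 points
- ρ = 0.7: 78.9% against 76.5%, a gain of 2.5
- ρ = 0.85: 97.0% against 96.6%, a gain of 0.4

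Simulation of rank ANCOVA minus Wilcoxon (10,000 trials per scenario, log-SD 0.40 and 0.45) gives 0.1-3.7 with normal log errors, 0.1-5.1 with t(3) errors, and -0.2 to 3.1 when 5% of patients have a threefold rise. These tests are pairwise, so the gain does not depend on what the other doses do.

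**Step 3. Why another model shows about 11 points.** With one pre-dose value the unadjusted variance is 2σ²(1-ρ) and the adjusted variance σ²(1-ρ²). At ρ = 0.5 these are 1.00σ² and 0.75σ². The baseline/log-ratio correlation is then -√(1 - 0.75/1.00) = -0.5, against -√(1 - 0.667/0.750) = -0.33 with two values. The Step 2 formula gives 54.6% against 43.6%, a gain of 11.1 points. A separate simulation set directly on the baseline/percent-change correlation (normal data, 24 per arm) agrees:

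| correlation | ANCOVA | Wilcoxon | Quade | Quade minus Wilcoxon |
|---|---|---|---|---|
| 0 | 79.7% | 76.8% | 76.5% | -0.3 |
| -0.3 | 79.8% | 72.8% | 75.9% | 3.1 |
| -0.5 | 79.5% | 64.7% | 75.5% | 10.8 |

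The larger figure is the more relevant for endpoints with one scheduled pre-dose sample, such as the NASH/fibrosis biomarkers and trough 7-α-C4 (Protocol 1.3, Week 0 only). It is indicative only, because their spread is not given.

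**Step 4. Chance imbalance.** A log-baseline difference of 0.5 SD is t = 0.5/√(2/24) = 1.73 on 46 df, so 9% of null comparisons reach it in one direction or the other. The shift in log ratio at exactly 0.5 SD is slope × 0.5 × σ√((1+ρ)/2):

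- ρ = 0.5: -0.333 × 0.5 × 0.364 = -0.061, about -5.9%
- ρ = 0.7: -0.176 × 0.5 × 0.387 = -0.034, about -3.4%
- ρ = 0.85: -0.081 × 0.5 × 0.404 = -0.016, about -1.6%

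Simulation over active-arm excesses of 0.5 SD or more moves Hodges-Lehmann by -1.9 to -6.5 percentage points with no true effect. In imbalanced comparisons, Wilcoxon false positives are 5.2-9.6% and rank ANCOVA 4.3-5.7%.

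**Step 5. Choice of test.** In the null scenarios of the Step 3 simulation (20 or 24 per arm; normal, lognormal or outlier data), ANCOVA gives 4.8-5.4%, Wilcoxon 4.5-5.5% and Quade 4.7-5.6%. The smaller p of ANCOVA and Wilcoxon gives 6.1-8.0%, and of ANCOVA and Quade 6.1-7.7%. Adding a better test therefore does not remove the latitude. Naming the lead does.

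**The case against.** The strongest reply has four parts.

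- **The ANCOVA stands.** SAP 8.7 states it without conditions, so the Wilcoxon reads naturally as supplementary. SAP 4.4 is a permissive general convention, while 8.7 is the endpoint-specific rule. This is fair. A reader might infer that the ANCOVA is to be discarded, or that the sponsor means to choose the better p-value. The documents support neither; they only leave the lead unstated.
- **The Wilcoxon is valid.** It holds about 5% over all null trials, and the raised rates appear only in the 9% or so with imbalance. This stands. The loss is in precision and conditional accuracy, not overall validity.
- **The switch protects against outliers.** With 5% threefold rises, simulated ANCOVA power was 34-48% against 45-91% for Wilcoxon. That tells against fixing the percent-change ANCOVA as sole lead with the rank result out of sight. It does not tell against adjusting the rank test. Comparisons involving the four-arm ANCOVA also depend on whether all doses share the effect: its shortfall against Wilcoxon under such rises was 9-46 points if they do, and 20-53 if only the compared dose works.
- **Little depends on it.** Testing is nominal, four unadjusted comparisons with placebo are planned, and MMRM and responder analyses also address ALT (SAP 8.7.1). Parts of SAP 8.1, 8.7.1 and the appendices are unreadable and may hold further detail. This keeps the severity low, but nothing readable supplies the criterion, the precedence or the covariate.

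Averaging the baseline also softens the point for ALT. Patients with ALT or AST above 60 IU/L "must have evidence of a stable ALT/AST over at least a 2-week time period prior to randomization", which may add a third value; the simulated gain is then -0.2 to 4.0 points.

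**Conclusion.** The point holds as a cheap improvement of low severity (could change). The fallback is triggered by an uncriterioned look, omits a covariate already collected and used in the ANCOVA, and has no stated standing if the results differ.

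A baseline-adjusted rank test gains about 0-5 power points over the unadjusted Wilcoxon for ALT with the averaged baseline, and up to about 11 at a baseline/percent-change correlation of -0.5. Best-of-two selection would give about 6-8% null error per comparison. Hodges-Lehmann moves by about 2 to 6.5 percentage points under chance imbalance of at least 0.5 SD. All of this rests on assumed ALT spread, correlation and effect.

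Two stronger conclusions are tempting. A reader might take 0-5 points as a price; it is a gain over the Wilcoxon, and a rank test shown in support costs the ANCOVA nothing. A reader might also conclude that the ANCOVA must be the sole lead or that a log-ratio model is required. The documents do not settle either: the first is a trade-off against outliers, the second a preference.

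**What to change.** In SAP 8.7, with the same wording carried to 8.8.1.1, 8.8.2, 8.8.3 and 8.10.3:

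1. Replace the unadjusted Wilcoxon with a baseline-adjusted rank test (rank ANCOVA or Quade), always run and always shown beside the ANCOVA. Keep Hodges-Lehmann with its 90% and 95% CIs, labelled as unadjusted for baseline.
2. State before unblinding which analysis leads, so that the choice does not depend on an unblinded look at the data. If a distribution check is to decide, give its criterion and do it on blinded data.

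An ANCOVA on ln(Week 12/baseline) is an optional addition where a ratio makes sense.

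The cost is SAP wording and minor programming, with no new data. There are two downsides. The adjusted rank test gives no percent-change estimate, so the ANCOVA and Hodges-Lehmann estimates are still needed. If the ANCOVA is named lead, it can lose much power when there are outliers, so the rank result must appear in the same table. If the rank test is named lead instead, it gives up about 2.6-4.5 points (Quade) or 1.4-3.5 points (four-arm rank ANCOVA) against the ANCOVA with normal or lognormal data at 24 per arm.
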